14.2 Potential Benefits of CYT107 to Patients with Sepsis

Sepsis is a disease with a high mortality for which there is no specific treatment other than traditional therapy of antibiotics and source control. The expected mortality in the septic patient population in the current study is approximately 40-45% at 60-90 days. Many of these deaths are due to failure to control the primary infection or development of new secondary infections. CYT107 reverses many of the sepsis-induced defects in host immunity and this improvement in host immunity will likely translate into decreased secondary infections, reduced ICU stay, and ultimately, improved survival. Although the present study is not powered to detect an improvement in survival, it is powered to demonstrate an effect of CYT107 to decrease new secondary infections which are a major cause of morbidity and mortality in sepsis.

Based upon data from both animal studies and clinical trials, we are extremely hopeful that CYT107 will improve morbidity and mortality in sepsis (12, 13, 14, 16, 18, 34). Studies from multiple independent laboratories using clinically relevant animal models of sepsis have shown that CYT107 improves survival (16, 18, 34). Finally, clinical trials of CYT107 in patients with cancer, bone marrow reconstitution, HIV, and JC virus induced progressive multi-focal

leukoencephalopathy have shown that CYT107 is well tolerated and efficacious. Clinical trials of CYT107 in oncology and in bone marrow reconstitution are being planned. Therefore, we believe that the risk benefit ratio is greatly in favor of use of CYT107 in patients with sepsis. As our group has argued passionately, we believe that CYT107 represents one of the most exciting immunotherapeutic agents in infectious disease in the last decade (6, 27, 39). If this proposed study is successful, it could radically change the way that physicians treat many infectious disorders including sepsis.

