
Secondary Biological Activity Study Endpoints
	
1) To determine pharmacokinetics (PK) including Cmax, area under the curve,(AUC) and T^{1/2} life of CYT107 in patients with severe sepsis and multiple organ failure who are treated with 10 µgs/kg ideal body weight using 2 different dosing regimens
 
2) Assessment of CYT107 immunogenicity by detection and quantification of binding antibodies and detection of neutralizing antibodies in positive samples
 
3) To determine pharmacodynamics (PD) including effects of CYT107 therapy to:
 
 i) improve absolute numbers and function of immune effector cells ii) changes in the absolute numbers of CD4+ and CD8+ T cells over the study period, standardized on the duration in the study. iii) Changes in the expression of the CYT107 receptor (CD127) on the surface of CD4+ and CD8+ T cells. iv) Effects of CYT107 on circulating monocyte HLA-DR expression v) Effects of CYT107 on whole blood LPS-stimulated TNF-α vi) Effects of CYT107 on anti-CD3/anti-CD28 stimulated peripheral blood mononuclear cells to produce IFN-γ. 
4) To determine effect of CYT107 to decrease the incidence of secondary infections. CYT107 has been highly effective in clinically relevant bacterial and fungal animal models of sepsis.(16)(18) We will compare the effect of CYT107 to reduce hospital-acquired secondary infections in CYT107 treated septic patients versus a control group of septic patients who receive placebo. The rate of hospital-acquired secondary infections at 42 days is roughly 35-40%.(20) We speculate that CYT107 will reduce the rate of secondary infections from 35-40% % to 25%.

---	--

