- Effects on anti-CD3/anti-CD28 stimulated peripheral blood mononuclear cells to produce IFN- γ .
- Effects to increase patient ALC to >1200 and to increase absolute CD4 and CD8 T cell counts.

3.2.3 To assess the impact on number and type of secondary infections:

CYT107 has been highly effective in improving survival in clinically relevant bacterial and fungal animal models of sepsis.(16,18,34) In addition, CYT107 has been effective in boosting immunity and reducing viral loads in patients with HIV and JC virus induced progressive multifocal leukoencephalopathy.(18,12,32) Most recently, CYT107 led to restoration of gut associated lymphoid tissue in HIV patients with a subsequent reduction in markers of inflammation.(31) Thus, we believe that CYT107 will improve host immunity and thereby lead to a decrease in hospital acquired secondary infections in septic patients.

Consequently, we hope to see a decrease in secondary opportunistic type bacterial and fungal infections in septic patients treated with CYT107 compared to septic patients who are treated with placebo (Control group). We will use the Center for Disease Control criteria for definition of ICU-acquired infections. Because it is often difficult to determine if a secondary hospital acquired infection is present, a panel of 3 experienced ICU physicians, “The Secondary Infection Evaluation Committee”, will be used to evaluate and grade whether a secondary hospital acquired infection is present. These 3 physicians will be blinded to patient treatment with CYT107 versus placebo. These 3 physicians will not be members of the investigative team but rather colleagues of the investigators. They will meet either in person or by teleconference once a month or as deemed necessary by the Investigator to judge secondary infections.

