4.2 Study Treatment

Up to thirty patients may be enrolled at 4 sites in the US, i.e., Vanderbilt, Ohio State, University of Florida, and Washington University School of Medicine, however, it is anticipated that the initial enrollment of 30 subjects will occur at Vanderbilt, Washington University and Limoges in France. (Note: the French sites may also enroll up to 30 patients such that a total of 30 evaluable patients will be available from the two countries). In the event that patient accrual is delayed in one country, all patients will be recruited from either the US or France alone. A computerized protocol will implement permuted block randomization in blocks of size three. This scheme ensures balance across the treatment groups for every third randomization. A maximum of 20 septic patients will be treated with CYT107 at a dose of 10µg/kg. There will be two dosing regimens as illustrated in Figure 8 (below). CYT107 will be administered intramuscularly at the dose of 10µg/kg (IBW), once or twice a week for a four week cycle. Ten septic patients will have CYT107 administered twice a week for 4 weeks. Ten septic patients will have two doses of CYT107 administered during the first week followed by one dose of CYT107 in conjunction with 1 dose of placebo for 3 additional weeks. Ten septic patients will receive placebo twice a week for four weeks along with routine standard of care per the clinical providers.

At approx. 48-120 hrs **after admission** for sepsis, those septic patients who meet the Inclusion/Exclusion criteria (see previous section) and provided written informed consent, will be entered into the study. The first dose of CYT107 (as indicated below) is at approx. 48-120 hrs after sepsis onset. The initial dose of study drug will be administered only in the ICU by the PI or research nurse. If patients have an INR greater than 2.5 or a platelet count less than 35,000, CYT107 will be administered by the subcutaneous route rather than by intra-muscular injection.

A staggered approach to CYT107 treatment will be used in which treatment will not be initiated in a newly enrolled patient until 24 hours after the previously enrolled patient has received the second dose of CYT107 without evidence of serious adverse event (SAE) occurrence.

In patients with coagulopathy (INR greater than 2.5 or a platelet count less than 35,000), CYT107 will be administrated subcutaneously.

Figure 8 Schematic study design of CYT107 Protocol

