4.3.2 Secondary Biological Activity Study Endpoints

- 1) *PK Sessions*: Briefly each patient will be sampled on day 1 and day 22 at 0 (pre-dose), 1, 3, 5, 7, 9 and 24 hrs post CYT107 administration. Main PK parameters will be assessed including Model-independent PK analysis will be used to estimate Tmax, Cmax, half-life, clearance and area-under-the-curve (AUC).
- 2) *Pharmacodynamics effects on immune markers*: The investigative sites will also examine the effect of CYT107 to restore function of immune effector cells in patients with sepsis.
 - i. Effect of CYT107 to increase the percentage of patients reaching an ALC>1200 in each dosing group. (An ALC of 1200 represents the lower limit of normal for most hospital laboratories.)
 - ii. Effect of CYT107 on absolute numbers of CD4⁺T and CD8⁺T over the study period,
 - iii. Effects on circulating monocyte HLA-DR expression
 - iv. Effects on whole blood LPS-stimulated TNF- α
 - v. Assessment of CYT107 immunogenicity by detection and quantification of binding antibodies and detection of neutralizing antibodies in positive samples.
- 3) *Incidence and type of opportunistic secondary infections*: We will compare the effect of CYT107 to reduce hospital-acquired secondary infections in CYT107 septic patients versus a control group of septic patients who receive placebo. The rate of hospital-acquire secondary infections at day 42 is ~ 40%.(20) We postulate that CYT107 will reduce the rate of secondary infections by ~ 30-40%. We will also examine other clinical measures in the CYT107-treated septic patients and compare outcomes including: SOFA scores, ICU free days, hospital free days, ventilator free days, decrease

in readmissions to ICU for recurrent infections. We will also record at approx. 60, 90, 180 and 365 day (1 year) general health status and survival.

All end points will be evaluated in a global analysis, pooling the results of the US and French sites using REDCap as the common patient database. Results will be visible to all investigative centers.

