9.0 Statistical Analysis

9.1 Sample Size

Sample size justification

The primary endpoint of this trial is to compare two different dosing regimens of CYT107 to increase the absolute lymphocyte count (ALC), a marker of immunosuppression in sepsis which correlates with mortality. Although CYT107 has not been previously been used to treat patients with sepsis, there are data on the effect of CYT107 to increase the absolute numbers of CD4 and CD8 T cells in patients with cancer and in patients with HIV (see Figs 2&6 and reference #14). As demonstrated in Figs 2 & 6, CYT107 at a dose of 10 micrograms/kg (the dose that will be used in the present study) has a very predictable effect to cause a doubling of the number of CD4 T cells which are a major component of the absolute lymphocyte count (ALC) in patients with HIV. This effect to increase the absolute numbers of CD4 T cells was consistent in almost all patients who were treated with CYT107. CYT107 has a similar effect (although not quite as pronounced) on CD8 T cells. Therefore, we anticipate that greater than 80% of septic patients who are treated with CYT107 at a dose of 10 micrograms/kg (either high frequency dosing regimen or the low frequency CYT107 dosing regimen) will increase their ALC by over 50% by day 42, whereas less than 20% of patients who receive placebo will exhibit such a change. Under these assumptions, a simulation-based power calculation as implemented using the primary analytical plan listed in section 9.3.2. In particular, the proposed study design (10 subjects per treatment arm) was found to have greater than 85% power to detect an equal or more extreme treatment effect. Thus, we believe that 10 patients per group is sufficient to show a statistically significant effect of CYT107 to increase the ALC by over 50%.

Two other major goals of the study are to establish the safety of CYT107 in patients with sepsis and to determine that the pharmacokinetics and pharmacodynamics are not significantly altered in septic patients. CYT107 has been administered to over 300 patients and has been well tolerated with a low incidence of side effects. (see Investigator's brochure.)

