9.2.4 Analysis of Other Biological Activity Endpoints

Descriptive statistics and simple inferential analyses (as described in 9.2.2) will be provided for all other biological activity endpoints.

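### Section 14.2 says the trial is powered to show fewer secondary infections; at the protocol's own rates, 20 CYT107 and 10 placebo patients give about 7-16% power

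*Protocol*

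**What the plan says.** Section 14.2 of the protocol, in the chapter on ethical considerations, separates two outcomes. It says that the study is not powered for survival, but that "it is powered to demonstrate an effect of CYT107 to decrease new secondary infections".

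The sample size section (9.1) makes no such claim. It concludes that "10 patients per group is sufficient to show a statistically significant effect of CYT107 to increase the ALC by over 50" percent, and gives power above 85% for that endpoint alone. On numbers treated, section 4.2 says "A maximum of 20 septic patients will be treated with CYT107", with ten more on placebo.

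The planning rates for secondary infections appear twice. The synopsis says "We speculate that CYT107 will reduce the rate of secondary infections from 35-40% % to 25" percent. Section 4.3.2 says "The rate of hospital-acquire secondary infections at day 42 is ~ 40" percent, and then "We postulate that CYT107 will reduce the rate of secondary infections by ~ 30-40" percent.

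Section 3.2.3 is more cautious: "we hope to see a decrease in secondary opportunistic type bacterial and fungal infections in septic patients treated with CYT107". On analysis, section 9.2.4 says "Descriptive statistics and simple inferential analyses (as described in 9.2.2) will be provided for all other biological activity endpoints". The SAP names no test for this endpoint.

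**The concern.** A statement that a trial is powered for an endpoint is a statement about its design, and it should rest on a calculation. Here there is none, and the numbers elsewhere in the protocol point the other way. The lymphocyte endpoint can be tested with 10 patients per arm because the assumed difference is 60 percentage points. The assumed difference for infections is 10 to 16 points.

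The sentence stands where the protocol argues benefit against risk, so it overstates what patients' participation can establish. It also affects how the result is read. If a trial described as powered for infections finds no significant difference, a reader may take that as evidence against an effect, when the trial had little chance of detecting one.

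**Working it through.** **Inputs**
- CYT107 20 patients (10 per frequency), placebo 10: section 4.2.
- Rates, placebo to CYT107: 35% to 25% and 40% to 25% (synopsis), with 37.5% to 25% as the midpoint. From section 4.3.2, with the reduction read as relative: 40% × (1 − 0.30) = 28% and 40% × (1 − 0.40) = 24%.
- Level 0.05 (SAP). The sidedness is not stated; two-sided is assumed.
- Test not fixed: the synopsis allows Fisher or Pearson chi-square for categorical variables, and section 9.2.2 uses logistic regression. All three are shown.
- Outcome assumed to be any secondary infection by day 42, yes or no, with the CYT107 arms pooled against placebo.

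**The plan's own power figure.** For the lymphocyte endpoint at 80%, 80% and 20% with 10 per arm, enumerating all outcomes under the three-arm likelihood ratio test (2 df) gives 86.0%. This agrees with the stated figure of more than 85%.

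**Power for secondary infections.** For every pair of counts (x of 10 on placebo, y of 20 on CYT107), add Bin(x; 10, p₀) × Bin(y; 20, p₁) whenever the test gives p < 0.05:

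| Placebo to CYT107 | Fisher | Chi-square, uncorrected | Likelihood ratio |
|---|---|---|---|
| 35% to 25% | 6.9% | 9.6% | 10.3% |
| 37.5% to 25% | 8.7% | 11.9% | 12.4% |
| 40% to 25% | 10.9% | 14.6% | 14.9% |
| 40% to 24% | 12.0% | 16.0% | 16.3% |
| 40% to 28% | 8.0% | 11.1% | 11.5% |

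The chance of a non-significant result is therefore 100 − 16.3 = 83.7% to 100 − 6.9 = 93.1%.

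**Other analyses**
- Three arms of 10, 2 df: 7.2-11.0% (chi-square), 11.6-16.2% (likelihood ratio).
- One CYT107 arm against placebo, 10 v 10: 2.2-3.9% (Fisher), 11.0-15.3% (likelihood ratio).
- Number of infections, assumed Poisson with mean −ln(1 − rate): 8.0-14.6% (exact), 11.5-19.1% (likelihood ratio).
- One-sided 0.05, chi-square: 15.8-25.0%.
- Enrolment doubled to 40 v 20: at most 21.4% (Fisher) or 25.6% (chi-square or likelihood ratio).

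**Size needed for 80% power.** With r CYT107 patients per placebo patient and p̄ = (p₀ + r·p₁)/(1 + r), the placebo group needs

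n₀ = [1.96·√((1 + 1/r)·p̄(1 − p̄)) + 0.84·√(p₀(1 − p₀) + p₁(1 − p₁)/r)]² / (p₀ − p₁)²

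and the total is (1 + r)·n₀. This gives about 265 (40% to 24%) to 657 (35% to 25%) at 1:1, and 292 to 729 at 2:1.

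**Precision.** The half-width of the 95% interval for the difference at 40% and 25% is 1.96 × √(0.25 × 0.75/20 + 0.40 × 0.60/10) = 0.358. Across the five pairs it is 0.351-0.362, or 35-36 points. That is more than twice the largest assumed effect of 16 points.

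**The case against.** The best defence concerns weight. The sentence is in a narrative section, the endpoint is secondary, and section 9.1 sizes the trial on lymphocyte response alone. No stopping or go/no-go rule uses the infection result, and section 4.1 makes a larger trial depend on safety and lymphocyte response. The misreading of a null result is therefore a risk, not a planned step. This stands and limits the severity. It does not make the sentence true.

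The 7-16% range depends on its assumptions. The SAP specifies pooling of the CYT107 arms only for mean lymphocyte count. The likelihood ratio test, which gives the top of the range, has an actual type I error of about 5.8-6.9% at this size for common rates of 25-40%. Any figure put into the protocol should therefore carry its test and assumptions. The other analyses stay far below 80%.

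Section 4.3.2 could be read as an absolute reduction. A fall from 40% to 10% gives 42.1% (Fisher) or 47.4% (chi-square). Only a fall to 0% gives adequate power, at 83.3% or 95.4%, and either fall contradicts the 25% in the synopsis.

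Replacement of non-evaluable patients could raise the number dosed above 30, but the doubled-enrolment result covers this. Infections are also followed to one year; the documents give no rates beyond day 42, so no power can be worked out for that window.

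**Conclusion.** The claim in section 14.2 is wrong as written. For a yes/no outcome by day 42, pooled CYT107 against placebo at 20 v 10 and two-sided 0.05, power is about 7-16% at the protocol's own rates, depending on the test. No analysis examined here comes near 80% under the relative reading of the reduction, even with twice the patients. Confidence is high, because the conclusion does not depend on which test is chosen. The correction should be made, but nothing in the sample size, primary analysis or conduct rests on the sentence.

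**What to change.** In section 14.2, delete the clause on secondary infections and say that the study is not powered to detect an effect on survival or on secondary infections. If a figure is added, give it with its basis: power of roughly 7-16% at the assumed rates, pooled CYT107 (20) against placebo (10), two-sided 0.05, depending on the test. Saying only that the study is not powered would also be enough.

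Report the pooled CYT107 minus placebo difference in infection rate with its 95% confidence interval, so that a non-significant result is not read as no effect. Section 9.2.2 already plans intervals for proportions, so this is a small addition.

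The cost is one sentence in 14.2 and one line in the results. The simple inference planned in 9.2.4 can stay.

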15.0 Regulatory considerations

15.1 Conditions for Conducting the Trial

15.1.1 Study Initiation Requirements

The protocol will have to be approved and signed by the representatives of the sponsor and by the investigators, as well as having been approved by each appropriate Ethics Committee or Institutional Review Board (IRB) in writing, before it can be initiated.

Prior to shipment of study drug, the investigator must provide Sponsor with at least the following documents:

- Signed final version of the protocol
- Curriculum vitae or other statement of qualification of the Principal Investigator (PI), any sub-investigator, and study coordinator.
- Ethics Committee/IRB approval letter, list of Ethics Committee (EC)/IRB members if the PI is the contact of the EC
- Signed and dated Clinical Trial Agreement between Sponsor and the institution and the investigator
- Completed local forms as required (Pre-study Financial Disclosure, etc...)

15.1.2 Study Personnel

The investigator should maintain a list of appropriately qualified persons who are delegated to perform significant study-related duties. In addition, the investigator should maintain a study delegation sheet to document signatures and initials of all persons authorized to perform any research related duties.

All medically-related decisions should be performed by a person medically qualified.

Information to the patient and/or LAR prior to consent should be given by a qualified physician or nurse member of the research team.

The PI is responsible for informing the patient's attending physician(s) when a patient has provided informed consent for study participation.

15.2 Protocol Amendments

Neither the investigators nor Revimmune can modify the study protocol without mutual agreement. Any change must be made following GCP and must be approved by the appropriate

Research Ethics Committee and Regulatory Authorities before implementation, with 2 exceptions:

- when necessary to eliminate apparent immediate hazard to the patient
- when the change involves logistical or administrative aspects of the study

15.3 Study Funding

The costs necessary to perform the study will be agreed with the investigator and/or the management of the study facility, and will be documented in a separate financial agreement that will be signed by the investigator and/or the management of the study facility Sponsor and any other Financial Co-Sponsor of the trial.

16. Reporting and publication

16.1 Confidentiality Agreement

Investigators agree to hold confidential all information regarding the product being tested, including the study methodology, and information developed during the course of this study, unless the information has previously been published. Investigators will ensure that all employees respect the same rules.

17. Archiving

The investigator is to keep the identification lists of patients for at least 15 years after the completion or premature termination of the study. The medical records of the patients in the trial together with other data are to be kept for as long as the hospital, or institution allows, but for a minimum of 15 years or according the local regulatory requirement.

The sponsor or subsequent owner is required to keep all other documentation for the life of the product studied. The archived data can be kept in electronic form, provided that a back-up copy is kept and that a paper copy can be provided if necessary.

The protocol, ethical and government approvals, together with all other documents concerning the study, including any audit and inspection certificates are all to be kept as part of the trial master reference file. All data about adverse events also needs to be kept in this trial master file.

All data should be available for inspection by the appropriate authorities on demand.

Appendices:

Appendix 1: Good Clinical Practice

ICH Topic E6

Guideline for Good Clinical Practice

The document is available on the following web site:

<http://www.emea.eu.int/pdfs/human/ich/013595en.pdf>

A copy of 'ICH Topic E6 Guideline for Good Clinical Practice', step 5 consolidated guideline will be provided in the study manual.

